15 16 17	ERR STA 15.1 15.2 15.3 15.4 15.5 15.6 DAT 16.1 16.2 16.3 16.4 16.5 16.6 16.7 ADN 17.1	OR! BOOKMARK NOT DEFINED. TISTICAL METHODS AND CONSIDERATIONS Data Sets Analyzed Demographic and Baseline Characteristics Analysis of Primary Endpoint Analysis of Secondary Endpoints Interim Analysis Error! Bookmark not defined. Sample Size and Randomization A COLLECTION, RETENTION AND MONITORING Data Collection Instruments. Data Management Procedures. Data Quality Control and Reporting Archival of Data Availability and Retention of Investigational Records Monitoring Subject Confidentiality. HINISTRATIVE, ETHICAL, REGULATORY CONSIDERATIONS	21 21 21 21 21 21 21 22 22 22 22 22 22 23 23 23

17.3	Informed Consent Form	24
17.4	Publications	24
17.5	Investigator Responsibilities	24

LIST OF ABBREVIATIONS

Add all other abbreviations referenced in the protocol and delete any not referenced in the protocol.

NS	Nigella sativa
CRF	case report form
SFDA	Saudi Food and Drug Authority
ICF	informed consent form
ICH	International Conference on Harmonisation
IEC	Independent Ethics Committee
IRB	Institutional Review Board
PI	Principal Investigator
SAE	serious adverse experience

PROTOCOL SYNOPSIS

TITLE	Effects of Nigella Sativa as a treatment of patients with upper respiratory tract infection caused by SARS-cononavirus-2: a prospective, randomized, open-label, controlled clinical study
SPONSOR	Self-sponsored
FUNDING ORGANIZATION	NA
NUMBER OF SITES	1
RATIONALE	The world is currently facing a crisis because of this potentially fatal COVID-19 outbreak with no proven efficacy yet of any drug therapy, while vaccination is not expected until 2021. Therefore, this study is intended to evaluate the potential efficacy for using Nigella sativa (NS) oil in patients with COVID-19.
STUDY DESIGN	Prospective, two-arm, parallel-group, randomised (1:1 allocation ratio), open-label, controlled, exploratory phase II clinical trial
PRIMARY OBJECTIVE	The primary objective is to assess the clinical efficacy as measured by the change in clinical recovery period over the 10 days treatment period.
SECONDARY OBJECTIVES	Assess the effect of NS on COVID-19 symptoms recovery.
NUMBER OF SUBJECTS	200
SUBJECT SELECTION CRITERIA	 Inclusion Criteria: Patients with mild COVID19 (defined as upper respiratory tract infection symptoms in the absence of clinical or radiological signs of pneumonia). -Adult (18 - 65 years old). Written informed consent by the patient (or legally authorized representative) prior to initiation of any study procedures. -All patients should understand and agree to comply with planned study procedures. Polymerase chain reaction (PCR)-confirmed infection with Severe Acute Respiratory Syndrome Coronavirus-2 (SARS-CoV-2). Exclusion Criteria:
	Patients with pneumonia or severe illness requiring admission to intensive care unit.Asymptomatic patients.

TEST PRODUCT,	 -Severe chronic kidney disease (i.e. estimated glomerular filtration rate [eGFR] < 30 mL/min) or end stage renal disease requiring dialysis -Severe chronic liver disease (Alanine transaminase [AIT] or Aspartate transaminase [AST] > 5 times the upper limit of normal). -Pregnancy or breast feeding. -Anticipated transfer within 72 hours to another hospital that is not a study site. -Allergy to the study medication. SFDA-licensed Marnys CUMINMAR Nigella sativa oil 500mg softgel cansules in oral twice daily dose for 10 days.
OF ADMINISTRATION	
CONTROL PRODUCT, DOSE AND ROUTE OF ADMINISTRATION	NA
DURATION OF SUBJECT PARTICIPATION AND DURATION OF STUDY	Subjects will be on study for up to 14 days Screening: up to 7 days Treatment: 10 days Follow-up: 14 days The total duration of the study is expected to be 12 months
CONCOMMITANT MEDICATIONS	Allowed: Any medication with no interaction with NS Prohibited: ANTICOAGULANT/ANTIPLATELET DRUGS, CNS DEPRESSANTS, CYCLOSPORINE, IMMUNOSUPPRESSANTS
EFFICACY EVALUATIONS	Clinical monitoring for 14 days
PRIMARY ENDPOINT	Proportion of patients who clinically recovered (defined as 3 days of no symptoms) within 14 days after date of onset of symptoms.
SECONDARY ENDPOINTS	 Improvement of Clinical Parameters: o Time to full clinical recovery o Time to progression to pneumonia or hypoxia o Duration of illness o Discharge to home o Normalization of chest radiograph. o Rate of complications: ICU admission, noninvasive ventilator, superadded infection

	o Death.
	- Normalization of Routine Laboratory Tests:
	o Complete Blood Count (CBC)
	o Erythrocyte sedimentation rate (ESR)
	o C-reactive protein
	o D-dimer
	o Liver function test
	o Renal function test
	o Lactate Dehydrogenase (LDH),
	o Immunoglobulins (IgA, IgE, IgG, IgM),
	o Compliments (c3, c4),
	o Chest X-ray, CT scan
	o COVID-19 PCR
	o Immune phenotype (CD3 T Cell, CD4 T Cell, CD8 T Cell, CD19 B Cell, CD20 B Cell, NK Cell).
OTHER EVALUATIONS	Inflammatory cytokines (IL-1β, IL-1Ra, IL-2, IL-6, IL-10, INF-alpha, INF-gamma, Eotaxin, RANTES & TNF-α).
SAFETY EVALUATIONS	Incidence of adverse events from the investigational drug or transfer to ICU
PLANNED INTERIM ANALYSES	When approximately 50% of patients have completed the study, an interim analysis for safety will be conducted by an independent data monitoring committee. Serious adverse events will be monitored by the research team on an ongoing basis throughout the study.
STATISTICS Primary Analysis Plan	After 10 days of intervention, the Proportion of patients who clinically recovered on day 14 will be compared with control group. Student t test will be used to compare means of both groups.
Rationale for Number of Subjects	To achieve a power of 80% and a two-tailed p-value of <0.05 of an assumed 40% difference between the proportion of patients with clinical cure among the NS group in comparison with the control group, a total of at least 200 patients assigned randomly into the two arms (ie 100 patients per arm) will be needed to be included in the study as calculated using G*Power version 3.1.9.2 (Heinrich-Heine-University Düsseldorf, Düsseldorf, Germany).

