8 STUDY TREATMENTS

8.1 Method of Assigning Subjects to Treatment Groups

Up to 200 eligible patients will be randomly assigned to treatment or control groups in a 1:1 ratio using a computer-generated randomization scheme developed by http://www.randomization.com.

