9.1.2 Demographics

Demographic information (date of birth, gender, race) will be recorded at Screening.

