9.1.3 Medical History

Relevant medical history, including history of current disease, other pertinent respiratory history, and information regarding underlying diseases will be recorded at Screening.

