10 EVALUATIONS BY VISIT

10.1 Visit 1 (Day 1)

- 1. Review the study with the subject (subject's legal representative) and obtain written informed consent.
- 2. Assign the subject a unique screening number.
- 3. Record demographics data.
- 4. Record medical history, diagnosis date.
- 5. Record concomitant medications.
- 6. Randomize subject,
- 7. Dispense study drug,
- 8. Initiate subject diary in CRF.

10.2 14 days monitoring

- 1. Record patients' symptoms
- 2. Record any Adverse Experiences and dosing compliance.
- 3. Concomitant medications review.

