14.5 Sample Size and Randomization

To achieve a power of 80% and a two-tailed p-value of <0.05 of an assumed 40% difference between the proportion of patients with clinical cure among the NS group in comparison with the control group, a total of at least 200 patients assigned randomly into the two arms (ie 100 patients per arm) will be needed to be included in the study as

calculated using G*Power version 3.1.9.2 (Heinrich-Heine-University Düsseldorf, Düsseldorf, Germany).

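### The primary comparison ignores prognostic data already collected before randomisation; prespecified covariate adjustment would be a cheap, modest gain in precision

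*Combined protocol and SAP*

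**What the plan says.** The Primary Analysis Plan in the synopsis says that "the Proportion of patients who clinically recovered on day 14 will be compared with control group" and names a Student t test. Section 14.3 repeats the t test and adds nothing. No covariate, regression model, stratified test or adjusted sensitivity analysis appears anywhere in the plan.

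Under section 8.1 patients are "randomly assigned to treatment or control groups in a 1:1 ratio using a computer-generated randomization scheme"; no stratification factor is given.

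Several prognostic variables are nevertheless collected at entry:

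- Section 9.1.2: "Demographic information (date of birth, gender, race) will be recorded at Screening".
- Section 9.1.3 covers the history of the current illness, and "information regarding underlying diseases will be recorded at Screening".
- Section 10.1 lists demographics as step 3 and "Record medical history, diagnosis date" as step 4. Randomisation is step 6.

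The symptom-onset date is not a listed Visit 1 item. The primary endpoint in section 5.1 (three symptom-free days inside a 14-day window) is counted from it, so it has to be captured.

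**The concern.** Age, comorbidity and stage of illness plausibly predict whether a patient with mild COVID-19 recovers within a fixed window. With 200 patients and no stratification, the arms can differ on these by chance, and the planned test makes no use of the information. Two things are at stake:

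- precision that could be had from data already on the case report form;
- a rule, fixed in advance, for what to do if the baseline table looks uneven. The trial is open-label, so an adjusted analysis added later would be chosen by people who know allocation and outcomes.

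Illness stage needs particular thought. Sections 6.2 and 6.3 require symptoms at entry but set no limit on time since onset. If the three symptom-free days must be completed within 14 days of onset, a patient still symptomatic on day 12 or later cannot meet the endpoint. Late entry would then partly determine the outcome.

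**Working it through.** **1. The plan's own figure.** Section 14.5 reads "To achieve a power of 80% and a two-tailed p-value of <0.05", with "an assumed 40% difference between the proportion of patients with clinical cure among the NS group", and arrives at "a total of at least 200 patients assigned randomly into the two arms (ie 100 patients per arm". No control rate is given, nor whether the 40% is absolute or relative.

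- Absolute 40 points: at most 24 per arm (29 with continuity correction) for assumed control rates of 5% to 60%. With 100 per arm, power exceeds 99.9%.
- Relative 40% from an assumed 50% (50% v 70%): 93 per arm (103 with continuity correction).
- Two-sided t test with standardised difference d = 0.40: exactly 100 per arm, power 80.4%.

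Only the last reproduces 100 exactly, so d = 0.40 is the reference below. The mismatch with the wording is a separate matter.

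**2. Gain from adjustment.** Inputs: N = 200 (section 14.5), four covariates, and R-squared, the share of outcome variance they explain. R-squared is assumed, because the documents give none.

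- Variance factor f = (1 − R²) × (1 + 4/193); the second term is the cost of estimating four coefficients.
- Effective N = 200 / f.
- Power = Φ(0.40 / √(0.02 f) − 1.96).

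| Assumed R² | f | Effective N | Power at d = 0.40 |
|---|---|---|---|
| unadjusted | 1 | 200 | 80.7% |
| 0 | 1.021 | 195.9 | 79.9% |
| 0.02 | 1.000 | 199.9 | 80.7% |
| 0.05 | 0.970 | 206.3 | 81.9% |
| 0.10 | 0.919 | 217.7 | 83.9% |
| 0.20 | 0.817 | 244.9 | 87.9% |

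Break-even is R² = 1 − 1/1.0207, about 0.02.

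**3. Simulation check.** 4,000 trials per setting, 100 per arm, assumed 50% v 70%; unadjusted difference against linear adjustment for four covariates with robust standard errors.

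| R² | Variance ratio | Power, unadjusted to adjusted |
|---|---|---|
| 0 | 1.02 | 82.8% to 81.5% |
| about 0.11 | 0.93 | 84.4% to 86.8% |
| about 0.21 | 0.82 | 83.0% to 89.5% |

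Neither analysis was biased, and type I error was 5% to 6% for both.

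**4. Chance imbalance.** The probability that one covariate differs by more than 0.2 SD is 2 × [1 − Φ(0.2/√(2/100))] = 2 × [1 − Φ(1.414)] = 15.7%. For at least one of four independent covariates it is 1 − 0.843⁴, about 50%. The resulting shift in the risk difference, with outcome SD 0.5, is 0.2 × √R² × 0.5: 1.4 points at R² = 0.02 and 3.6 points at R² = 0.13. The unadjusted standard error at 50% v 70% is √(0.25/100 + 0.21/100), or 6.8 points.

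**5. Days ill at entry, taken alone.** Assumptions: lognormal illness duration, median roughly 6 to 12 days, log-SD 0.35 to 0.5; patients still symptomatic at entry; no treatment effect.

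| Anchor | Entry days | R², roughly | Direction |
|---|---|---|---|
| Symptom onset | 1-7 | 0-2% | negative |
| Symptom onset | 1-10 | 2-8% | negative |
| Symptom onset | 1-14 | 10-20% | negative |
| Study day 14 | 1-7 | 0-7% | positive |

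Section 5.1 uses the first anchor. The synopsis wording about recovery on day 14, following ten days of intervention, can be read as the second. The covariate's sign reverses between them.

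**The case against.** The strongest reply is that nothing is broken. Randomisation makes the unadjusted difference unbiased, and its standard error already includes chance imbalance. A single prespecified test leaves no covariates to choose. All of that stands. A reader might infer from the 16% or 50% imbalance figures that the primary result is at risk of bias; steps 3 and 4 do not support that.

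Second, adjustment has a price. Four covariates cost about 2% in variance, and below R-squared of about 0.02 the trade is a small loss. A reader might also take the R-squared 0.20 row as a promise of some 50 extra patients. That value is assumed, and the population is narrow (mild disease, ages 18 to 65, one site). Even then the net figure is 245, not 250.

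Third, days ill is a weak predictor if entry is early, because the clock in section 5.1 starts at onset rather than entry. This stands for entry in the first week. It does not hold generally, because the criteria admit later entrants.

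Fourth, recovery may be common. At an assumed 85% to 95%, only 10 to 30 of 200 patients would not recover, and a logistic model with arm and four covariates could fail to converge. That is a reason to name a fallback, not to leave adjustment out.

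Finally, if the 40% is an absolute difference, power is near 100% anyway and adjustment only narrows the interval. This also stands.

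**Conclusion.** The point holds as one of efficiency and prespecification, not of validity. The primary analysis is unadjusted in an unstratified trial, and usable baseline variables are recorded before randomisation. The plausible effect runs from a loss of about one point of power, if the covariates predict nothing, to a gain of about three points at R-squared 0.10 and seven at 0.20, taking d = 0.40 as the design effect. These figures rest entirely on assumed R-squared values. A 0.2 SD imbalance would move the estimate by about 1.4 to 3.6 points at R-squared 2% to 13%, well inside the unadjusted standard error. Days ill contributes materially only if late entrants are enrolled, and its direction is undefined until the day-14 anchor is settled. The change is a cheap improvement. The documents do not support calling the gain free or the present test biased.

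**What to change.** 1. First make the synopsis and section 5.1 agree on whether day 14 counts from symptom onset or from study entry. Adjustment does not repair that ambiguity.
2. In section 14.3 and the synopsis, prespecify a small covariate set: age, sex, any underlying disease (yes/no, with the qualifying conditions listed) and days from symptom onset to randomisation.
3. Add the onset date to the Visit 1 list and record it for every patient. The endpoint needs it anyway, and the timing covariate then has a single definition. State a rule for missing covariate values.
4. Report a standardised risk difference from a logistic model with a 95% CI (delta method or bootstrap).
5. Name the fallback for sparse events or non-convergence, for example linear adjustment with robust standard errors, or a stated shorter covariate list.
6. Keep the unadjusted difference in proportions, with its interval, as a sensitivity analysis.

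Cost: protocol wording, one explicit field on the case report form and a few lines of code, with no extra patients. The statistical downside is about 2% more variance if the covariates turn out to be uninformative.

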3 STUDY OBJECTIVES

3.1 Primary Objective

The primary objective is to assess the clinical efficacy as measured by the change in clinical recovery period over the 10 days treatment period.

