5 CRITERIA FOR EVALUATION

5.1 Primary Efficacy Endpoint

Proportion of patients who clinically recovered (defined as 3 days of no symptoms) within 14 days after date of onset of symptoms.

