5.2 Secondary Efficacy Endpoints

- Improvement of Clinical Parameters:
- o Time to full clinical recovery
- o Time to progression to pneumonia or hypoxia
- o Duration of illness
- o Discharge to home
- o Normalization of chest radiograph.

o Rate of complications: ICU admission, noninvasive ventilator, superadded infection o Death.

- Normalization of Routine Laboratory Tests:
- o Complete Blood Count (CBC)

o Erythrocyte sedimentation rate (ESR)

o C-reactive protein

o D-dimer

o Liver function test

o Renal function test

o Lactate Dehydrogenase (LDH),

o Immunoglobulins (IgA, IgE, IgG, IgM),

o Compliments (c3, c4),

o Chest X-ray, CT scan

o COVID-19 PCR

o Immune phenotype (CD3 T Cell, CD4 T Cell, CD8 T Cell, CD19 B Cell, CD20 B Cell, NK Cell)

- Additional:

o Inflammatory cytokines (IL-1β, IL-1Ra, IL-2, IL-6, IL-10, INF-alpha, INF-gamma, Eotaxin, RANTES & TNF-α).

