14.3 Analysis of Primary Endpoint

Student t test will be used for significance analysis.

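### The primary objective is a duration, the primary endpoint a proportion and the primary test a comparison of means, so the primary result is not uniquely fixed

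*Combined protocol and SAP*

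**What the plan says.** The statements that should define one primary result are these.

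- **Objective (synopsis and 3.1):** to "assess the clinical efficacy as measured by the change in clinical recovery period over the 10 days treatment period". This is a length of time.
- **Endpoint (synopsis and 5.1):** "Proportion of patients who clinically recovered (defined as 3 days of no symptoms) within 14 days after date of onset of symptoms". This is yes or no for each patient.
- **Analysis (synopsis, Primary Analysis Plan):** "the Proportion of patients who clinically recovered on day 14 will be compared with control group", and in the next sentence "Student t test will be used to compare means of both groups".
- **Analysis (14.3):** "Student t test will be used for significance analysis". No variable, effect estimate or interval is given. Section 14.4 uses the same sentence for every secondary endpoint.
- **Sample size (14.5):** "To achieve a power of 80% and a two-tailed p-value of <0.05", for an assumed 40% difference between proportions with clinical cure, a term used only in the sample-size text. The result is 100 per arm.

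The secondary list in 5.2 includes "Time to full clinical recovery" and duration of illness, which is the quantity that the primary objective describes. It also includes "Rate of complications: ICU admission, noninvasive ventilator, superadded infection" and death. The synopsis describes the trial as open-label and exploratory.

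**The concern.** Objective, endpoint and test point to different kinds of variable. A patient has one recovery period, so the change named in 3.1 can only mean a difference between arms in recovery time, and a t test fits that reading naturally. The endpoint and the sample size fit a comparison of proportions. One analyst could report mean recovery days and cite 3.1, the synopsis and 14.3. Another could report the proportion and cite 5.1, the synopsis and 14.5. No passage says which governs.

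The synopsis adds a smaller ambiguity within the proportion: recovered on day 14 is not the same as recovered within 14 days of symptom onset, because patients enter at different times after onset.

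At stake is whether a result at the 0.05 level carries its stated error rate. In an open-label trial, a choice of variable made after the data are visible cannot be shown to be independent of them.

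Mean recovery days has its own difficulty. It has no value for a patient not recovered when follow-up ends, and the plan gives no rule for such patients.

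**Working it through.** **1. The plan's own figure: 100 per arm, 80% power, two-sided 0.05.**

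Two proportions, 40 points apart: n = [1.960·√(2p̄q̄) + 0.842·√(p₁q₁ + p₂q₂)]² / (p₁ − p₂)². The control rate is not stated. For 30% v 70%, n = (1.386 + 0.545)² / 0.16 = 23.3, so 24 per arm. Over control rates of 5% to 60% the answer is 15 to 24 per arm (20 to 29 with continuity correction), not 100.

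A 40% relative difference: control rates of 48% and 49% give 103 and 98 per arm, so 100 is matched only near an unstated rate of that size (or near 50% with continuity correction, 103 per arm).

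Two means, standardised difference 0.40: the normal approximation is 2(1.960 + 0.842)² / 0.40² = 98.1, so 99. The exact t solution is 99.1, so 100 per arm.

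The stated size therefore fits a comparison of means exactly, although the text speaks of proportions. This is an inference, since no SD or standardised effect is given. It shows only that the reading as means is plausible.

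**2. Is a t test on the 0/1 endpoint harmful?**

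With 100 per arm:

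- z = (p₁ − p₂) / √(p̄q̄·2/100)
- t = (p₁ − p₂) / √(s²·2/100), with s² = 100(p₁q₁ + p₂q₂)/198

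Exact enumeration at event rates of 10% to 90%, in steps of ten points, gives a t-test size of 0.049 to 0.056. Its decision differs from that of chi-square with probability at most 0.0016. The tests split, for example, at 39 v 26 recovered: z = 0.13/0.06624 = 1.963 against 1.960, and t = 0.13/0.06593 = 1.9718 against 1.9720. For practical purposes they are the same test.

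**3. What does the unsettled variable cost?**

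Assumptions, since the protocol gives no recovery-time figures: Weibull recovery times with shape 1.6 and median 9 or 12 days, 100 per arm, 14 days of follow-up, no treatment effect, each test at 0.05.

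| Candidates | At least one significant |
|---|---|
| Proportion, or mean days with unrecovered patients set to 14 | 8 to 9% |
| Proportion, or mean days among recovered patients | 9 to 10% |
| All three | 11 to 12% |

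A log-normal model (median 10 or 12 days from randomisation, entry up to 7 or 10 days after onset) gives 8 to 9% for the onset-based proportion or mean duration capped at 14 days. Adding the day-14 proportion gives 11 to 12%. For comparison, independent tests would give 1 − 0.95² = 9.75% and 1 − 0.95³ = 14.3%.

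The choice can also hide an effect. With a recovery hazard ratio of 1.5 in the Weibull model, power is roughly 58 to 64% on the proportion and 10 to 22% on mean days among recovered patients.

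**4. Sparse secondary outcomes.**

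At event rates of 1%, 2%, 3% and 5% the t-test size is 0.014, 0.040, 0.045 and 0.044. For 4 v 0 events of 100, p is 0.044 (t), 0.043 (chi-square), 0.12 (Fisher) and 0.104 (Boschloo).

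**The case against.** The strongest reply is that a proportion is plainly meant. It is the endpoint in the synopsis and in 5.1, the quantity in the first sentence of the Primary Analysis Plan, and the basis of 14.5. The heading of 14.3 ties its t test to the primary endpoint, and recovery time is listed as secondary. Only the objective points to a duration, and on a proportion the named test does no real damage. Most of this stands, and it lowers the severity. It does not remove the mismatch, because the objective and the instruction to compare means remain in the current text unreconciled. The exploratory label does not dispose of it either, since 14.5 sets 80% power and a 0.05 threshold.

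Three stronger readings are tempting and are not supported.

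- A reader might infer that the plan lets the team report whichever variable is significant. It does not; it is unclear, which is different. The figures in step 3 show what selection would cost if it happened. Neither way of averaging recovery days used there appears in the protocol.
- A reader might infer that the t test is invalid for the endpoint. At 100 per arm, step 2 shows otherwise.
- A reader might infer that the t test inflates error for ICU admission, ventilation or death. At event rates of 1 to 5% it is conservative, and at 4 v 0 it agrees with chi-square. Exact methods are preferable there, but no inflation is shown.

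**Conclusion.** The mismatch is real and sits in the current text. The objective, the endpoint with its sample-size basis, and the test do not describe the same quantity. A proportion is the dominant reading, but the text does not exclude mean recovery days, so the primary result is not uniquely fixed.

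The size of the problem is modest: about 8 to 10% false positives with two candidates, and 11 to 12% with three, in place of 5%. Those figures require both that someone selects among the variables and that recovery times resemble the assumed distributions. The finding of an unsettled variable needs neither assumption. This is a should-fix.

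**What to change.** 1. **Synopsis and 14.3:** state that the primary analysis is the difference between arms in the proportion recovered as defined in 5.1, with a 95% confidence interval (Newcombe or Miettinen-Nurminen) and a two-sided chi-square test at 0.05.
2. **Synopsis:** reconcile the day-14 wording of the Primary Analysis Plan with the onset-based definition in 5.1, so that there is one time origin.
3. **Synopsis objective and 3.1:** name that same proportion, and leave recovery time as secondary.
4. **14.4, durations:** replace the t test for time to full recovery, duration of illness and time to progression with a time-to-event method (Kaplan-Meier and log-rank), censoring patients without the event at the end of follow-up.
5. **14.4, complications:** report ICU admission, ventilation, superadded infection and death as counts by arm with exact intervals.

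The cost is a few sentences, made as an amendment under 16.1 before outcomes are compared by arm. No patients are added. The daily symptom record over 14 days in 10.2 already supplies the recovery dates.
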